All endpoints achieved within 30 day period after end of study drug treatment:

- Number of subjects with complete remission (defined as confirmed platelet response and absence of exacerbation)^{1,2}
- Number of (subjects with) exacerbations of TTP (defined as recurrent thrombocytopenia following a confirmed platelet response and requiring a re-initiation of daily PE treatment after ≥ 1 day but ≤ 30 days after the last daily PE), and time to first exacerbation of TTP
- Number of subjects relapsing of TTP (defined as *de novo* event of TTP that occurs later than 30 days after the last daily PE)
- Number of daily PE sessions, number of plasma units administered and number of days of daily PE
- Resolution of non-focal neurological symptoms as defined by neurocognitive function at complete remission, measured by a neurocognitive test battery
- Resolution or improvement (improvement of ≥ 1 grade in the Common Terminology Criteria for Adverse Events (CTCAE) v4.0 scale) of TTP-related signs and symptoms as captured on physical examination and as adverse events, at complete remission and at end of the study drug treatment period (including tapering) (by number of

unique subjects and by total number of adverse events (AEs))

- Total mortality within the PE treatment period and within the subsequent study drug treatment period (including tapering)
- Incidence of PE treatment-related AEs, such as, but not restricted to: haemorrhage from catheter insertion, sepsis, catheter thrombosis, pneumothorax, fluid overload, hypoxia, hypotension, anaphylactoid reactions and transfusion related acute lung injury (TRALI)
- Incidence and severity of ALX-0081 treatment-emergent AEs and relationship to study drug
- Development of anti-drug antibodies (ADA) \leq 30 days post-last study drug treatment
- PK and PD profile

Tertiary Endpoints

[REDACTED]

[REDACTED]

[REDACTED]

[REDACTED]

[REDACTED]

[REDACTED]

[REDACTED]

Study Design

This is a Phase II multicentre, single-blinded, parallel design, randomised, placebo-controlled study.

After confirmation of eligibility to study participation, subjects will be randomised in a ratio of 1:1 to either receive ALX-0081 or placebo as adjunctive therapy to PE (Figure 1).

[figure not shown]

Figure 1: Treatment flow chart.
First PE on study: see section 4.2

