7.2 Treatment and Dosing Regimen for Study Drug

The study drug will be administered as adjunctive treatment at specific times relative to the PE procedures. The study drug consists of 10 mg of ALX-0081 or placebo, once or twice daily as explained below (Table 8).

Subjects will receive a first i.v. bolus of 10 mg ALX-0081 or placebo via push injection within 6h, but not later than 15 min prior to the initiation of PE on study (i.e., the very first PE session, if the subject was randomised prior to the initiation of PE, or the second PE session, if the subject was randomised after one, single PE session; see section 4.2). This first PE on study is followed by s.c. administration of 10 mg study drug within 30 minutes after the end of the PE procedure.

During the complete PE treatment period (including tapering and PE given for exacerbations), study drug will be administered daily via s.c. injections.

- If 1 PE per day is scheduled, 10 mg of study drug will be administered within 30 minutes after the end of the PE procedure.
- If 2 PEs per day are scheduled, 10 mg of study drug will be administered within 30 minutes after the end of each PE procedure. The maximum total daily dose of study drug is hence 20 mg.
- If less than 1 PE per day is scheduled (i.e. during a tapering regimen), 10 mg of study drug will be administered daily. On days with a PE, study drug administration should be within 30 minutes after the end of the PE procedure; on days without PE, study drug administration should be 24 h (\pm 1 h) after previous administration

Daily s.c. study drug administration of 10 mg will continue for 30 days after the very last PE (including tapering).

Maximum treatment duration with study drug will be limited to 90 days after first administration of study drug.

In case of exacerbation of TTP (after \geq 1 day but \leq 30 days after the last daily PE), standard treatment (PE) should be re-initiated and daily s.c. administration of study drug continued.^a The “study drug post-PE” period (for 30 days after the very last PE, see Figure 5 further below) will re-commence once PE is again stopped. Maximum treatment duration with study drug will be limited to 90 days after first administration of study drug.

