BNP or NT proBNP (local lab)			X				X	X
Brain damage markers (NSE, Sβ100) (central lab)			X				X	X
PK (central lab)	X	X	X					If applicable ^a
RICO (central lab)	X	X	X					If applicable ^a
vWF (central lab)	X	X	X	X	X	X	X	X
FVIII chromogene (central lab)	X	X	X	X	X	X	X	X
ADA (central lab)			X	X	X	X	X	X
ADAMTS13 and anti-ADAMTS13 antibody titre (central lab)			X				X	X
Recuperate AE diary	X	X	X	X	X	X	X	If applicable ^b

^a i.e. during treatment phase with study drug.^b i.e. post-hospital discharge

Blood chemistry includes glucose, AST, ALT, LDH, CRP, creatinine, urea (BUN), uric acid, protein, albumin, haemoglobin, Na, K, Ca, Mg and Cl. Haematology includes haemoglobin, haematocrit, MCV, MCH, MCHC, full blood count including RBC, WBC, differential, reticulocytes, platelet count and, if available, immature platelet fraction. Coagulation variables include fibrinogen, aPTT, PT, INR, vWF:Ag and FVIII (chromogene or alternative method)

Precaution to be taken for cessation of study drug administration:

As described in section 8.1.2, ADAMTS13 and anti-ADAMTS13 antibody titre will be measured from blood sampling at 1-week and 3-weeks after the last day of PE (including tapering). Note that the 1-week and 3-weeks after the last day of PE (including tapering) sampling may be done at the weekly visit, even if not exactly 1 or 3 weeks.

The resulting data will be provided to the Investigator for information at the end of the study. In case an investigator has no access to similar assays and availability of ADAMTS13 and anti-ADAMTS13 antibody titre are considered essential for clinical decision making, an ad hoc determination of the results can be organised (under supervision of the country coordinator).

Platelets and LDH will be measured from blood sampling on days 3 and 7 following the conclusion of study drug administration. If at any time the platelet count falls below 70% of the last platelet count prior to cessation of study drug administration, with concomitant LDH > 1.5 X ULN: the subject will be considered at risk of a relapse and she/he will need to be closely monitored by the site staff.

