Complete remission: Complete remission is defined as recovery of platelets (confirmed by platelets  $\geq 150,000/\mu\text{L}$  and LDH  $\leq 2 \times \text{ULN}$  at 48 hrs after initial platelet response) and absence of exacerbation.

Initial platelet recovery: Date of initial platelet recovery is defined as the first occurrence of platelets  $\geq 150,000/\mu\text{L}$  which is **confirmed** 48 hours later by platelets  $\geq 150,000/\mu\text{L}$  and LDH  $\leq 2 \times \text{ULN}$ . For example, if platelets reach  $\geq 150,000/\mu\text{L}$  on Day 5, are not confirmed at Day 7, reach  $\geq 150,000/\mu\text{L}$  again on Day 10 and are confirmed at Day 12, the initial platelet recovery occurs on Day 10. Initial platelet recovery and confirmation dates will be determined using the actual lab results, following standardisation to consistent units.

Time to Response: Time to response will be calculated as the number of days, hours and minutes (represented by number of days with two significant digits after the decimal point) from study drug administration to initial platelet recovery, as defined above. An

---

observation is censored if the observation does not meet the defined time interval of 30 days, due to any cause of loss-to follow-up (including death), or endpoint not being reached.

Subjects that attain confirmed platelet response:

Time-to-Response = [Date and time (hrs, min) of initial platelet recovery] – [Date and time (hrs, min) of first study drug administration]

Exacerbation: Exacerbation of TTP is defined as recurrent thrombocytopenia following a confirmed platelet response and requiring a re-initiation of daily PE treatment  $\geq 1$  day but  $\leq 30$  days after the last daily PE.

Relapse: Defined as de novo event of TTP that occurs later than 30 days after the last daily PE.

First PE: Defined as start of PE.

First on-study PE: Defined as first PE received after randomisation.

In case first on-study PE is not first PE, then first on-study PE should be started within 24 hours (after the end) of the first PE. If not it is considered major protocol deviation.

Overall duration of study treatment exposure (days): Defined as date of last dose of study treatment – date of first dose of study treatment + 1

Duration of study treatment exposure during daily PE (days): Defined as date of last dose of study treatment during the daily PE period – date of first dose of study treatment during the daily PE period + 1

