### 6.3.2 Secondary Efficacy Variables

#### *Secondary Endpoints*

All endpoints achieved within 30 day period after end of study drug treatment:

- Number and percentage of subjects with complete remission (defined as confirmed platelet response and absence of exacerbation)
- Number and percentage of (subjects with) exacerbations of TTP (defined as recurrent thrombocytopenia following a confirmed platelet response and requiring a re-initiation of daily PE treatment after  $\geq 1$  day but  $\leq 30$  days after the last daily PE) and time to first exacerbation of TTP
- Number of daily PE sessions, number of total volume of plasma administered and number of days of daily PE
- Total mortality within the PE treatment period and within the subsequent study drug treatment period (including tapering)
- Number and percentage of subjects relapsing of TTP (defined as *de novo* event of TTP that occurs later than 30 days after the last daily PE)
- Number and percentage of subjects with platelets  $\geq 150,000/\mu$ L at day 30 of study drug administration (last treatment day visit) and one month follow-up time point
- Resolution or improvement (improvement of  $\geq 1$  grade in the CTCAE v4.0 scale) of TTP-related signs and symptoms as captured on physical examination and as adverse events, at complete remission and at end of the study drug treatment period (including tapering) (by number of unique subjects and by total number of AEs)
- Incidence of PE treatment-related AEs, such as, but not restricted to: haemorrhage from catheter insertion, sepsis, catheter thrombosis, pneumothorax, fluid overload, hypoxia, hypotension, anaphylactoid reactions and TRALI

---

This study has been statistically powered for the primary endpoint. No adjustment for multiplicity has been applied to the exploratory analysis for the secondary variables. All analysis will be performed on the ITT and PP populations and any p-values presented for secondary efficacy variables are purely exploratory (e.g. comparison of the number and percent of subjects with complete remission, exacerbations, relapse and daily PEs).

The number and percentage of subjects with complete remission at one month post first administration of study treatment, along with the exact binomial CI of the percentage will be presented by treatment group, overall and by ADAMTS13 activity  $< 5\%$  vs.  $\geq 5\%$  at baseline.

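### Complete remission is lost only through exacerbation, so on the planned course a relapse in the month after study drug leaves it intact; the SAP's read-out one month after first dose also comes before that month begins

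*Protocol*

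**What the plan says.** **Complete remission.** Protocol synopsis and 4.1.2: "Number of subjects with complete remission (defined as confirmed platelet response and absence of exacerbation". SAP 6.3.2 repeats it: "Number and percentage of subjects with complete remission (defined as confirmed platelet response and absence of exacerbation". The derived variable in SAP Section 3 also ends with "at 48 hrs after initial platelet response) and absence of exacerbation". Relapse is not named as a reason to lose remission in any of these places.

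**The two recurrence labels.** An exacerbation is a recurrence "requiring a re-initiation of daily PE treatment after ≥ 1 day but ≤ 30 days after the last daily PE". A relapse is an "event of TTP that occurs later than 30 days after the last daily PE"; SAP Section 3 agrees: "Defined as de novo event of TTP that occurs later than 30 days after the last daily PE". Both labels are dated from the last daily PE, not from study drug.

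**Study drug.** Protocol 7.2: "Daily s.c. study drug administration of 10 mg will continue for 30 days after the very last PE (including tapering". A cap of 90 days from the first dose applies. The same section notes that tapering prolongs study drug, so a relapse can fall before the drug course is over.

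**Read-out.** In both documents the secondary endpoints stand under a heading that runs to 30 days after the end of study drug. The analysis text of SAP 6.3.2, however, tabulates complete remission, exacerbation and relapse one month after the first dose. A further row, for exacerbation and relapse combined, has no stated time point.

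**After drug stops.** Protocol 8.1.3 sets platelet and LDH checks on days 3 and 7. If the values move in a specified way, "the subject will be considered at risk of a relapse and she/he will need to be closely monitored by the site staff".

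**The concern.** A reader will take complete remission, under a heading that reaches 30 days past the end of drug, to mean that the subject was still free of TTP at that point. On the planned course it cannot mean that. The only event that removes a subject from the count becomes impossible no later than the day the drug stops. Someone back on daily PE two weeks later is still counted as remitted.

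This matters because the off-drug month is where the data can begin to separate prevention of recurrence from postponement until withdrawal. If the drug only postpones some recurrences, those subjects lose nothing under this definition, while placebo subjects whose recurrences come earlier, as exacerbations, do lose remission.

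The SAP time point adds to this. At one month after first dose the off-drug month lies in the future, so the tabulated figures would not show off-drug recurrence even if relapse did void remission.

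**Working it through.** **1. The plan's own figure.** The only design number used here is N = 110 (protocol 10.4, SAP 6.1.4). Hazard ratio = 6/3.36 = 1.786. By the Schoenfeld formula, events = (1.960 + 0.842)² / (0.25 × (ln 1.786)²) = 93.39. Allowing for 15% loss, 93.39/0.85 = 109.9, or 110. (Rounding up to 94 events first gives 111.) At 1:1 that is about 55 per arm, so one subject is 1/55 = 1.8 percentage points of an arm's remission rate. Nothing else below depends on N.

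**2. Calendar of the labels.** Take the first dose as day 0, L = day of last daily PE and T = days of tapering. Then:

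- drug end D = min(L + T + 30, 90), or earlier if stopped early
- end of exacerbation window X = L + 30
- off-drug month = D + 1 to D + 30

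The documents give no expected L. L = 6 borrows the assumed control median time-to-response as an illustration; the other values show the range.

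| Case | D | X | Off-drug month | Off-drug days labelled relapse | Off-drug days labelled exacerbation |
|---|---|---|---|---|---|
| L = 3, no taper | 33 | 33 | 34–63 | 30 | 0 |
| L = 6, no taper | 36 | 36 | 37–66 | 30 | 0 |
| L = 60, no taper | 90 | 90 | 91–120 | 30 | 0 |
| L = 6, taper 7 days | 43 | 36 | 44–73 | 30 | 0 |
| L = 70 (cap) | 90 | 100 | 91–120 | 20 | 10 |
| L = 75 (cap) | 90 | 105 | 91–120 | 15 | 15 |
| L = 6, drug stopped day 16 | 16 | 36 | 17–46 | 10 | 20 |

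Without tapering D = X for every L up to 60, so all 30 off-drug days carry the relapse label. With 7 days of tapering the last 7 on-drug days (43 − 36) carry it too. The last three rows are the exceptions: under the cap or after an early stop, part of the off-drug month can still void remission.

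**3. The SAP time point.** The read-out is day 30 after first dose.

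- On the planned course the off-drug month starts on day L + T + 31, always later than day 30. With L = 6 and no taper it starts on day 37, 7 days after the read-out.
- A relapse must fall after day L + 30, and L cannot precede the first dose. No relapse can be counted by day 30, whatever the arm.
- Even the exacerbation window is cut short: with L = 6 it runs to day 36, so its last 6 days are unseen.

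**4. Other wording.** SAP Section 4, in the neurocognitive item, describes remission as at least 30 days without needing PE. A subject who recurs on day 31 already satisfies that, so it does not close the gap.

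**The case against.** The strongest defence is that the definition is deliberate. It is explicit, carries citations, is used consistently, and describes resolution of the index episode. Relapse is treated as a new event with its own endpoint. The event is not lost either: the SAP gives the combined exacerbation and relapse row by arm with exact intervals and a time-to-first plot, the share with platelets at or above 150,000/µL at one-month follow-up, and relapse for up to a year. All of this is secondary, with p-values labelled exploratory.

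Much of that stands. Keeping the two labels apart is legitimate, and the combined row is the one that speaks to prevention versus delay. But that row is undated and does not alter the remission count. The platelet row describes one visit, not whether daily PE was restarted. The relapse row at one month after first dose is empty by construction.

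Four stronger readings are tempting, and the documents do not support them:

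- *The off-drug month can never affect the endpoint.* Not so under the 90-day cap or early drug stop, because the label follows PE and not drug.
- *The protocol expects recurrence on withdrawal.* The day 3 and day 7 checks in 8.1.3 are a monitoring precaution; protocol 2.5.2 hopes that the drug may prevent relapses.
- *The endpoint favours ALX-0081.* That holds only if recurrence is delayed, which is unknown.
- *The bias can be sized.* Suppose all subjects respond, control exacerbation risk is 30%, the drug suppresses 80% of exacerbations, and every suppressed recurrence returns off drug. Then remission would be 94% against 70% as defined, and 70% against 70% counting relapse. None of those rates is in the documents, and the sum assumes no placebo relapse in the off-drug month. Any such relapse would narrow the gap between the definitions.

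**Conclusion.** The point holds in bounded form. For a subject on the planned course, with or without tapering, a recurrence needing daily PE in the 30 days after end of drug is a relapse and leaves complete remission intact. Subjects who reach the 90-day cap with daily PE lasting past day 60, or who stop drug early, are partial exceptions.

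Separately, SAP 6.3.2 contradicts its own heading on when complete remission, exacerbation and relapse are read, and the time point in its analysis text precedes the off-drug month.

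The direction of any distortion is conditional: the endpoint would overstate benefit if ALX-0081 delays rather than prevents recurrence. Its size cannot be derived from the documents; each affected subject moves an arm's rate by about 1.8 points. The primary endpoint and the sample size are untouched. It is worth correcting because a reported remission rate will be read at face value and the correction is cheap.

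**What to change.** 1. In SAP 6.3.2, replace the time point of one month after first dose with the 1-month follow-up visit (30 days after end of study drug) for complete remission, exacerbation and relapse, and give the combined row the same time point.
2. Report complete remission as confirmed platelet response with neither exacerbation nor relapse up to that visit, beside the current definition, with a matching derived variable in SAP Section 3.
3. Keep the current definition as the anchor for endpoints assessed at complete remission (neurocognition, TTP signs and symptoms). The follow-up neurocognitive test is due around day 3 after the last dose, before the wider definition could be known.

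No clinical rule changes and nothing new is collected. PE sessions are recorded for up to a year (protocol 8.2.1.1.1), relapse PE has its own schedule (protocol 8.1.3, Table 14), and the main report already waits for the last subject's 1-month follow-up visit (protocol 12.10). The cost is one extra derivation and possibly a lower reported remission rate. Secondary p-values remain exploratory.

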2. BACKGROUND INFORMATION

2.1 Introduction

2.1.1 Role of vWF in Platelet Aggregation

The multimeric plasma protein vWF is essential for recruiting circulating platelets to the damaged vessel wall upon vascular injury. This recruitment is mediated through binding of the vWF A1-domain with the platelet receptor glycoprotein GPIb-IX-V.

Upon expression by endothelial cells, vWF is secreted into the circulation as ultra-large multimers or ultra-large vWF (ULvWF). These multimers are processed into smaller regular sized multimers through enzymatic cleavage by ADAMTS13. In these regular sized multimers of vWF, the GPIb-IX-V platelet receptor binding site in the A1 domain is cryptic and will not spontaneously react with platelets. A conformational activation of the GPIb-IX-V platelet receptor binding site in the A1 domain is triggered by immobilisation or under conditions of shear stress. This then results in platelet adhesion and subsequently in thrombus formation.

2.1.2 Role of vWF and vWF Processing in Pathophysiology of TTP

TTP is a rare and life-threatening disorder of the blood coagulation system, in which accumulation of ULvWF multimers has been implicated, leading to an increased risk of thrombus formation in small blood vessels due to excessive platelet aggregation. The condition is characterised by systemic platelet aggregation in the microcirculation, producing fluctuating ischaemia in many organs. If sustained, this may cause tissue infarction, associated with profound thrombocytopenia and erythrocyte fragmentation.

ULvWF multimers have the natural ability to spontaneously interact with the platelet receptor GPIb-IX-V. In healthy subjects, these ULvWF multimers are immediately processed into regular sized vWF multimers via cleavage by ADAMTS13. However, in patients with TTP, processing of the ULvWF multimers is impaired, resulting in the persistence of the constitutively active A1 domain of the ULvWF which readily interacts with the GPIb-IX-V platelet receptor. This eventually results in formation of the characteristic blood clots found in the TTP patient population.

2.1.3 Role of vWF in Other Pathologies

Coronary heart disease

In patients without impairment of vWF processing, the initial pro-thrombotic activity of the ULvWF multimers is immediately pacified by their processing into regular sized multimers via cleavage by ADAMTS13. The resulting regular sized multimers have an inactive A1 domain which becomes only “reactivated” for binding the platelet GPIb-IX-V receptor upon immobilisation and through a conformational change under shear stress. This “reactivation” of the A1 domain becomes a critical component in the unwanted thrombus formation in patients with coronary heart disease undergoing a percutaneous coronary intervention (PCI) procedure. In coronary arteries, blood flow conditions are recognised as high shear, which triggers the said conformational change of the A1 domain in regular sized vWF-multimers, resulting in platelet adhesion to the injury of the coronary artery vessel wall (caused by the PCI procedure) and subsequent thrombus formation. Therefore, Ablynx also performed clinical studies to develop ALX-0081 for the prevention of thrombosis in coronary heart disease, and more specifically acute coronary syndrome (ACS).

von Willebrand disease

In von Willebrand disease (vWD), there are 3 kinds of disorders. Type 1 of the disease is pertinent when the vWF is quantitatively reduced, but not absent, with a resulting symptomatology that consists of non-severe mucosal bleeding or bruising. Type 2 vWD concerns patients who carry gene mutations/deletions resulting in qualitatively abnormal vWF. A subcategory of Type 2 patients (Type 2N), have genetic alterations provoking a markedly decreased binding affinity for FVIII. Type 2, with the exception of Type 2N, has variable bleeding, usually mild to moderate and is in general restricted to limited bruising and mucosal bleeding. In Type 3 vWD virtually no vWF is present. In patients with Type 2N and Type 3 vWD the carrier function of vWF for FVIII is compromised. These patients may present with severe bleeding phenotype resembling haemophilia A, mainly provoked by the loss of FVIII. In symptomatic patients (i.e. Type 2N and 3) or in cases where clinical interventions could lead to an increased bleeding risk (i.e. tooth extraction, surgeries) vWF concentrate is used as therapeutic, stabilising the patient’s bleeding risk and restoring the normal function of vWF/FVIII-mediated haemostasis.

